25.5.2 Extension Study Clinical Efficacy Analyses (see Section 24.6)

25.5.2.1 ACR CRISS (American College of Rheumatology Composite Response Index for clinical trials in early diffuse cutaneous Systemic Sclerosis)

As per Section 24.6.1, step 1 of ACR CRISS is tabulated and summarized descriptively for both treatment groups at initial study day 1, day 84 (week 12) and day 168 (week 24) of the initial study. Step 1 of ACR CRISS will be additionally tabulated and summarized descriptively for both treatment groups for extension study day 84 (week 36) and extension study day 168 (week 48).

As per Section 24.6.1, step 2 of ACR CRISS calculates changes from baseline in the predicted probability of improvement and is being applied and summarized descriptively for both treatment groups at initial study day 84 (week 12) and day 168 (week 24). Step 2 of ACR CRISS will be additionally applied and summarized descriptively for both treatment groups at extension study day 84 (week 36) and extension study day 168 (week 48).

25.5.2.2 Additional Assessments for Clinical Efficacy (see Section 24.6.2)

As per Section 24.6.2, the results of mRSS score and change from baseline for study day 84 (week 12) and day 168 (week 24) of the initial study are summarized without imputation for missing values for both treatment groups. Additional results of mRSS and change from baseline will be summarized without imputation for missing values for both treatment groups for extension study day 84 (week 36) and extension study day 168 (week 48).

As per Section 24.6.2, the percent predicted FVC and DLCO results and change from screening at study day 28 (week 4), day 56 (week 8), day 84 (week 12), day 112 (week 16), day 140 (week 20) and day 168 (week 24) of the initial study are summarized descriptively without imputation for missing values for both treatment groups. Additional percent predicted FVC and DLCO results and change from screening will be summarized descriptively without imputation for missing values for both treatment groups for extension study day 84 (week 36) and extension study day 168 (week 48).

As per Section 24.6.2, total lung capacity results and change from screening at study day 84 (week 12) and study day 168 (week 24) of the initial study are summarized descriptively without imputation for missing values for both treatment groups. Additional total lung capacity results and change from screening will be summarized descriptively without imputation for missing values for both treatment groups for extension study day 84 (week 36) and extension study day 168 (week 48).

As per Section 24.6.2, HRCT chest scan Goh scoring of ILD severity and change from baseline at initial study day 168 (week 24) are summarized descriptively for both treatment groups. HRCT chest scan Goh scoring of ILD severity and change from both baseline and initial study day 168 (week 24) will be summarized descriptively for extension study day 168 (week 48) for both treatment groups.

As per Section 24.6.2, the results for each of the disease-status scales Mahler BDI/TDI, SHAQ, PtGA and MDGA and changes from baseline at study day 84 (week 12) and study day 168 (week 24) of the initial study are summarized descriptively without imputation for missing values for both treatment groups. The results for each of these disease-status scales Mahler

BDI/TDI, SHAQ, PtGA and MDGA and changes baseline will be summarized descriptively without imputation for missing values for both treatment groups for extension study day 84 (week 36) and extension study day 168 (week 48).

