7.0 STUDY DESIGN

7.1 Overview

This is a phase 2 open-label, safety and tolerability pilot study of oral ixazomib in patients with scleroderma-ILD (SSc-ILD). Planned enrollment will be 12 patients who have been seen in the Mayo Clinic Arizona Scleroderma program among whom will be 6 participants already taking SSc-ILD background medication mycophenolate (MMF) at stable dose for at least 3 months, and 6 participants who either have not taken a SSc-ILD background medication within 3 months of study screening or by the time of study screening will complete medication washout of medications being taken for SSc-ILD other than MMF. The number of study candidates needing to washout medications other than MMF is anticipated to be very low based on the low prevalence of medicines other than MMF used clinically for the treatment of scleroderma-ILD. No study candidate already taking MMF will be asked to wash out MMF. Eligible participants include male and female adult patients at least 18 years of age, fulfilling the 2013 American College of Rheumatology (ACR)/European League Against Rheumatism (EULAR) criteria for systemic sclerosis/scleroderma [151] and having disease duration \leq 60 months based on first non-Raynaud's phenomenon manifestation. ILD is based on features observed from the participant's HRCT chest scan obtained within 3 months prior to either medication washout or screening visit, as applicable. Studyscreening

will include pulmonary function testing demonstrating FVC \geq 45% predicted and DLCO \geq 40% predicted, which will also be determined to be stable measurements as compared with previous pulmonary function testing obtained clinically within the prior 3-12 months. For the 6 study participants who are taking stable dose background MMF, the MMF will be continued at the same dose during the study. MMF will be prescribed as routine clinical care and will not be provided as part of the study. All 12 participants will be administered oral ixazomib. Ixazomib dose modification or interruption will be allowed for safety or tolerability reasons at any time during the study. Any patient who permanently and prematurely discontinues study treatment will also be discontinued from the study.

There are four study periods (all durations are in calendar days):

- **Washout Period:** \leq 90 days:
 - **Participants who are taking background SSc-ILD medication other than MMF at screening:**

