24.0 STATISTICAL METHODS and ANALYSES

24.1 Analysis Population

The primary analysis population will be:

- **Safety Population:** All patients who provide written informed consent, and receive at least one dose of ixazomib

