24.2 Hypothesis Testing

No formal hypothesis testing will be done.

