24.6.2 Additional Assessments for Clinical Efficacy

Analysis of these additional efficacy assessments will be based on the safety population. Clinical efficacy assessments will include each of the individual components of ACR CRISS as follows:

- mRSS (modified Rodnan skin score)
- FVC % predicted
- HAQ-DI (Health Assessment Questionnaire-Disability Index)
- PtGA (Patient Global
- MDGA (Physician Global Assessment)

Additional clinical efficacy measures include:

- DLCO % predicted
- HRCT chest scan ILD severity using the Goh scoring method
- Patient reported outcome Mahler Baseline/Transitional Dyspnea Index (Mahler BDI/TDI).

The results of mRSS score and changes from baseline at study day 84 (week 12) and study day 168 (week 24) will be summarized without imputation for missing values.

The percent predicted FVC and DLCO results and change from screening at study day 28 (week 4), day 56 (week 8), day 84 (week 12), day 112 (week 16), day 140 (week 20) and study day 168 (week 24) will be summarized descriptively without imputation for missing values. Total lung capacity results and change from screening at study day 84 (week 12) and study day 168 (week 24) will be summarized descriptively without imputation for missing values.

HRCT chest scan Goh scoring of ILD severity and change from baseline at study day 168 (week 24) will be summarized descriptively.

The results for each of the disease-status scales Mahler BDI/TDI, SHAQ, PtGA and MDGA and changes from baseline at study day 84 (week 12) and study day 168 (week 24) will be summarized descriptively without imputation for missing values.

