25.1 Eligibility

Only participants continuing to use ixazomib and completing the initial 24-week safety and tolerability study will be eligible to continue their participation in a 24-week extension study. Participants proceeding on to the extension study will not complete the initial study follow-up day 196-203 (week 28-29) office visit (see 18.3.11).

In the 24-week extension study, ixazomib dosing will continue orally on days 1, 8, and 15 of 28-day treatment cycle for 6 cycles. The first dose of ixazomib for each cycle will continue to be taken as part of the extension study office visits assessments and procedures.

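### Week-36 and week-48 efficacy is summarised as change from original baseline in extension entrants only, beside week 12-24 summaries of a wider set, with no matched comparison except for HRCT

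*Combined protocol and SAP*

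**What the plan says.** Section 7.1: "Planned enrollment will be 12 patients", six on background MMF and six on no background SSc-ILD medication. Section 24.2: "No formal hypothesis testing will be done".

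For efficacy to week 24, Section 24.6.2 states: "Analysis of these additional efficacy assessments will be based on the safety population". Section 24.1 defines that population as those who consent and "receive at least one dose of ixazomib".

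Entry to the extension is narrower. Section 25.1: "Only participants continuing to use ixazomib and completing the initial 24-week safety and tolerability study will be eligible to continue". Entry is also optional, because Sections 17.2.1 to 17.2.3 schedule a closing visit for participants who do not go on to it.

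Section 25.5.2 restates the week 12-24 summaries and adds weeks 36 and 48. For mRSS: "Additional results of mRSS and change from baseline will be summarized without imputation for missing values for both treatment groups". FVC, DLCO and total lung capacity are handled the same way from screening. The Mahler index, SHAQ, PtGA and MDGA are handled the same way from baseline, and ACR CRISS is added at the same two visits. HRCT is the one measure with a second reference point: "change from both baseline and initial study day 168 (week 24) will be summarized descriptively for extension study day 168 (week 48").

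**The concern.** A reader who sees change from baseline at weeks 12, 24, 36 and 48 for each treatment group will naturally read across the row and take the step from week 24 to week 36 or 48 as what happened on continued treatment. That holds only if the same people are averaged throughout. Here the later columns can contain fewer people, chosen by their own or the investigator's decision to continue. Because the scale stays anchored at the original baseline, the change of membership does not show in the mean.

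What is at stake is the interpretation of durability between 24 and 48 weeks. In a descriptive study the displayed summary is the result, and with six participants per group one or two non-entrants can move it noticeably.

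**Working it through.** The plan states no figure that could be reproduced here: it gives no SD, no expected entry rate and no target change. The check therefore has two parts, who can be counted at each visit and how far the mean can move.

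**Who can contribute**

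| Participants | Weeks 12-24 | Weeks 36 and 48 |
|---|---|---|
| Complete week 24, enter extension | yes | yes, while on drug |
| Complete week 24, do not enter | yes | no; last visit is day 196-203 (18.3.11), without mRSS or lung function |
| Stop drug before week 24 | visits before stopping; whether the early-discontinuation visit counts as week 24 is not stated (15.0) | no; follow-up ends between day 168 and day 196-203 (15.1.5) |
| Stop drug during extension | yes | later visits summarised separately (25.5.4); whether the early visit using week-48 procedures (25.3.1) counts as week 48 is not stated |

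So the set at week 36 is smaller than at week 24 whenever any completer does not enter.

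**How far the mean can move**

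Let n participants in a group contribute at week 24, of whom k do not enter. Let m_E and m_N be the mean changes from baseline of entrants and non-entrants, and d = m_N − m_E. Then

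- week-24 mean = [(n − k) m_E + k m_N] / n = m_E + (k/n) d
- if nobody changes after week 24, the week-48 mean is m_E
- apparent movement = (k/n) d, with no true change.

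A higher mRSS is worse, so a positive d (non-entrants did worse) gives apparent improvement and a negative d gives apparent worsening.

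Example, with assumed values: four entrants each at −6 and two non-entrants each at 0. The week-24 mean is (4 × −6 + 2 × 0)/6 = −4 and the week-48 mean is −6. The table shows 2.0 points of further improvement although nobody changed. The formula agrees: (2/6) × 6 = 2.0.

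Apparent mRSS improvement for a group of six, d assumed:

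| Non-entrants | d = −6 | d = 0 | d = 3 | d = 6 | d = 9 |
|---|---|---|---|---|---|
| 0 of 6 | 0 | 0 | 0 | 0 | 0 |
| 1 of 6 | −1.0 | 0 | 0.5 | 1.0 | 1.5 |
| 2 of 6 | −2.0 | 0 | 1.0 | 2.0 | 3.0 |
| 3 of 6 | −3.0 | 0 | 1.5 | 3.0 | 4.5 |

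**Dependence on why people do not enter**

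A simulation (40,000 runs, 2 of 6 not entering, SD of mRSS change assumed to be 7, no true change after week 24) varied the correlation between the tendency not to enter and a poor response:

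| Correlation | Mean shift in mRSS (negative = apparent improvement) | Runs showing apparent improvement |
|---|---|---|
| −0.3 | +1.00 | 31% |
| 0 | 0.0 | 50% |
| 0.3 | −0.99 | 69% |
| 0.5 | −1.67 | 82% |
| 1.0 | −3.35 | 100% |

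At zero correlation the 5-95% range of the shift is about −3.3 to +3.3 points. In groups this small, the change of membership disturbs the row even when non-entry is unrelated to response.

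**With matched participants**

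If the same entrants are shown at every visit, or change is taken from their own week-24 value, the spurious movement is zero by construction in every scenario above.

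**The case against.** The strongest reply is that direction and size both depend on facts not yet known. If all completers enter, nothing shifts; if non-entrants did better, the later means look worse. That stands. A reader might infer that the week-48 results will look like further improvement, or are biased towards benefit. The documents do not support this, because they give neither an entry rate nor any information on how non-entrants will have responded.

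A reader might also infer that intolerant or worsening participants leave the mean exactly between weeks 24 and 36. Section 15.0 takes such participants off drug and out of the study during the first 24 weeks, and their later visits are summarised under Section 24.8. They are in the week-24 mean only if the early-discontinuation visit is counted as week 24, which is not stated. The group certain to be counted at week 24 and absent afterwards is completers who do not enter, and the stopping rules say nothing about their response.

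Nor are these summaries the only new efficacy information from the extension: HRCT has its change from week 24, and Section 25.5.4 summarises those who stop during the extension.

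Finally, the study is an uncontrolled pilot with no testing, the objectives in Section 6 cover six cycles, no plot or week-24-to-48 contrast is specified, and Section 25.5.1 plans patient disposition by group. All of this limits the importance. But disposition counts would reveal a smaller denominator without recovering the matched comparison, and the plan names no other display from which to judge durability on these measures.

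**Conclusion.** The point holds as a defect of display. For every efficacy measure except HRCT, Section 25.5.2 offers no way to separate what happened during the extension from who entered it. The distortion is (k/n) × d and can go either way: towards apparent benefit if non-entrants did worse, towards apparent worsening if they did better, and nil if all enter or the two sets do not differ. The 2.0-point mRSS example assumes that all six in a group contribute at week 24, that two do not enter, and that the gap is 6 points. The simulated range assumes an SD of 7. None of these values comes from the documents except the group size. No hypothesis test or primary safety conclusion is affected. The change is worth making because the plan already takes a second reference point for HRCT, and because Section 24.8.2 measures post-discontinuation change from the early-discontinuation visit.

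**What to change.** In Sections 25.5.2.1 and 25.5.2.2:

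- Give n at each visit, and label weeks 36 and 48 as *participants who entered the extension*.
- Show entrants' own week-12 and week-24 values, including ACR CRISS, beside their week-36 and week-48 values.
- Add change from week 24 for mRSS, FVC, DLCO, total lung capacity, SHAQ, PtGA and MDGA. The Mahler TDI is already a transition index, so show entrants' scores at each visit instead.
- Show non-entrants' week-24 results on a separate line.
- State whether early-discontinuation visits that use the day-168 procedures count as week 24 (initial study) or week 48 (extension).

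The cost is a few table rows from data already collected, with no added visits. The 48-week picture may look less favourable than it would under the present wording.

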25.5.3 Extension Study Post-Discontinuation Assessments for Safety

Identical to Section 24.7 Post-Discontinuation Assessments for Safety for the 24-week initial study, participants in the 24-week extension study who prematurely and permanently discontinue ixazomib study medication and continue monitoring with extension study post-discontinuation visits (see Section 25.4.2) will be included for the analysis of post-discontinuation safety data. Summaries of AEs, deaths, and patient disposition will be presented.

Safety outcome measures used will include, but will not be limited to:

- Treatment-emergent (not ixazomib) AEs
- Treatment-emergent (not ixazomib) SAEs
- Treatment-emergent (not ixazomib) treatment-related AEs
- Treatment-emergent (not ixazomib) treatment-related SAEs
- Treatment-emergent (not ixazomib) changes in clinical laboratory measures
- Treatment emergent (not ixazomib) changes in patient vital signs
- Treatment emergent (not ixazomib) changes in UCLA SCTC GIT 2.0 questionnaire

25.5.4 Extension Study Post-Discontinuation Clinical Efficacy Analysis

Participants who prematurely and permanently discontinue ixazomib study medication during the extension study and who continue monitoring with extension study post-discontinuation visits (see Section 25.4.2) will be included for the analysis of post-discontinuation clinical efficacy data.

25.5.4.1 ACR CRISS (American College of Rheumatology Composite Response Index for clinical trials in early diffuse cutaneous systemic Sclerosis)

Step 1 ACR CRISS will be tabulated and summarized descriptively for extension study post-discontinuation visit 3 (ESPD day 84) and post-discontinuation visit 6 (ESPD day 168) as applicable and the extension study final post-discontinuation visit.

Step 2 ACR CRISS calculates changes from baseline in the predicted probability of improvement and will be applied and summarized descriptively for extension study post-discontinuation visit 3 (ESPD day 84) and post-discontinuation visit 6 (ESPD day 168) as applicable and the extension study final post-discontinuation visit.

25.5.4.2 Additional Assessments for Extension Study Post-Discontinuation Clinical Efficacy

Additional results of mRSS and change from baseline will be summarized without imputation for missing values for both treatment groups for extension study post-discontinuation visit 3 (ESPD day 84) and post-discontinuation visit 6 (ESPD day 168) as applicable and the extension study final post-discontinuation visit.

Additional percent predicted FVC and DLCO results and change from screening will be summarized descriptively without imputation for missing values for both treatment groups for extension study post-discontinuation visit 3 (ESPD day 84) and post-discontinuation visit 6 (ESPD day 168) as applicable and the extension study final post-discontinuation visit.

Additional total lung capacity results and change from screening will be summarized descriptively without imputation for missing values for both treatment groups for extension study post-discontinuation visit 3 (ESPD day 84) and post-discontinuation visit 6 (ESPD day 168) as applicable and the extension study final post-discontinuation visit.

As per Section 24.6.2, HRCT chest scan Goh scoring of ILD severity and change from baseline at initial study day 168 (week 24) are summarized descriptively for both treatment groups. HRCT chest scan Goh scoring of ILD severity and change from both baseline and initial study day 168 (week 24) for both treatment groups will be summarized descriptively for extension study final post-discontinuation visit.

Bibliography

1. Steen, V.D. and T.A. Medsger, Jr., *Severe organ involvement in systemic sclerosis with diffuse scleroderma*. *Arthritis Rheum*, 2000. **43**(11): p. 2437-44.
2. Rubio-Rivas, M., et al., *Mortality and survival in systemic sclerosis: Systematic review and meta-analysis*. *Seminars in Arthritis and Rheumatism*, 2014. **44**(2): p. 208-219.
3. Tyndall, A.J., et al., *Causes and risk factors for death in systemic sclerosis: a study from the EULAR Scleroderma Trials and Research (EUSTAR) database*. *Ann Rheum Dis*, 2010. **69**(10): p. 1809-15.
4. Steen, V.D. and T.A. Medsger, *Changes in causes of death in systemic sclerosis, 1972-2002*. *Ann Rheum Dis*, 2007. **66**(7): p. 940-4.
5. Altman, R.D., et al., *Predictors of survival in systemic sclerosis (Scleroderma)*. *Arthritis & Rheumatism*, 1991. **34**(4): p. 403-413.
